### 3.2. Study population, inclusion, and exclusion criteria

All patients admitted to the clinical centers for emergent or elective surgery will be screened for eligibility criteria. In the case of elective surgery, patients will be screened 1 day before the intervention, and in case of emergency surgery, just before or within 12 h after the intervention.

#### **Inclusion criteria:**

- Age over 40 years;
- Major surgery required;
- High risk of postoperative VTE;
- Caprini score of 11 or more (at extremely high risk of VTE);
- Informed consent is given.

Age over 40 years is suggested as an inclusion criterion by the Russian National Guidelines on VTE prevention, which recognize these patients as a standard high-risk group if undergoing major surgery.

Major surgery is recognized as any procedure under general or regional anesthesia with the leg motor block with a duration of 45 min and more that are equal to major surgery (>45 min) or laparoscopic surgery (>45 min) in the Caprini model.

Primary risk assessment for postoperative VTE should be made according to the rules of the Russian National Guidelines, and only patients at high-risk (major surgery in patients of 40–60 years old with additional individual risk factors, or major surgery in

patients of 60 and more years old independent of additional risk factors) will be screened for eligibility according to the Caprini score.

The Caprini score should be assessed twice: at the baseline screening before inclusion and before discharge or after death. It will be allowed to include patients with supposed scores of  $\geq 11$  (e.g., supposed cancer, supposed long bed rest, supposed CHF, CVD, etc.), but not less than 9. The final assessment of concomitant diseases as risk factors will be performed by an invited specialist. The maximal Caprini score will be taken into account.

**Exclusion criteria:** acute DVT at baseline; performed IVC plication or implanted IVC filter; regular preoperative anticoagulation; postoperative anticoagulation needed at therapeutic doses; absence of anticoagulation  $>5$  days after surgery; coagulopathy (not related to DIC syndrome); thrombocytopenia; hemorrhagic diathesis; lower limb soft-tissue infection; lower limb skin lesion; ankle-brachial index  $<0.6$ .

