### **3.1. Randomization, Stratification, and Minimizing Bias**

The randomization should be performed independently for both clinical centers and should be based on the number of hospital medical records. After screening, only eligible patients will be randomized. If the last digit in the number of the hospital medical record is even, the patient should be allocated to the IPC group, and if odd, to the control group. If the last digit in the number of the hospital medical record is zero, the previous digit should be used. Both clinical centers contain multiple medical departments of different specialties, and the numbering of the medical records is performed sequentially through all departments. It starts at the beginning of the year (for example, the first medical record in 2017 is 1/17) and finishes at the end of the year. Taking into account the large admission rate to all medical departments, there is an extremely low probability that two consistently included patients would have sequential medical records. To reduce the bias of the deliberate non-inclusion of the patients with higher VTE risk in the IPC group all non-eligible subjects should be repeatedly evaluated for exclusion criteria by the Data Monitoring Committee.

After allocation to the group, the patient will be assigned an individual code, containing his index number, initials, and year of birth (for example, 1IV1961). This individual code will be used in all study documentation. The allocation list will be stored by the investigator. The blinded expert who will perform a duplex ultrasound scan (DUS) would not have access to the primary medical record or allocation list; he will use only individual patients code for identification. Also, to achieve blindness, most duplex scans will be performed in a separate room away from the patient's bed. If it will be impossible to transfer a patient to the room, the DUS will be performed at the bed, but the IPC device will be removed before the blinded expert's visit. A schematic diagram of the patient allocations is shown in Figure 2.

**Figure 1.** Scheme of the randomization and blindness.

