### **3.3. Patient's withdrawal from the study**

Patient's withdrawal from the study will be possible in case of the patient's refusal from further participation, the occurrence of serious adverse events necessitating early termination of study procedures, as well as meeting the criteria for patient's withdrawal from the study. The criteria for withdrawal are as follows: the occurrence of any VTE event, considered as a primary or secondary endpoint; the occurrence of major or non-major clinically relevant bleeding, considered as secondary endpoints, required the discontinuation of LMWH administration; the occurrence of leg skin injury, considered as a secondary endpoint; required discontinuation of IPC application; the occurrence of any clinical condition required discontinuation of IPC or ECS application (e.g., leg ischemia, compartment syndrome); the occurrence of any clinical condition that required discontinuation of LMWH administration (e.g., thrombocytopenia, allergic reaction); the occurrence of any clinical condition that required changes in the VTE prophylaxis modality (e.g., change in dose and type of anticoagulation); and the occurrence of any exclusion criteria after randomization.

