### **3.5. Endpoints and definitions**

**Primary endpoint:** asymptomatic venous thrombosis of the lower limbs detected by DUS during inpatient treatment.

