#### **5.4. Examination during inpatient treatment**

The following data on surgical procedure should be obtained from the medical records after intervention: the surgical profile (e.g., abdominal, thoracic, neck, pelvis, cranial), type of surgery (open, endoscopic, endoscopy assisted), urgency of surgery (emergent = performed in 0–2 h after admission, urgent = performed in 0–6 days after admission, elective = performed independently at the time of admission), radicalism of surgery (radical, palliative), type of anesthesia (general, regional, combined), surgery duration, blood loss, and intraoperative infusion.

The routine clinical examination of the patient will be performed in a daily manner with special attention to the possible complications, such as DVT, SVT, PE, bleeding, and leg skin injury. IPC sleeves should be removed for 15–20 mins every day for skin inspection and investigation of pedal pulsation. Consultation of any relevant specialist

(cardiologist, neurologist, pulmonologist, infections) should be performed if any complication or development of new co-morbidity will be observed during the follow-up.

DUS should be performed every 3–5 days after surgery and in emergency manner if any clinical suspicion for DVT or SVT appeared. In an emergency manner, DUS may be performed by a blinded expert or specialist on duty on weekend and holidays. However, all conclusions of non-investigational medical staff must be verified by a blinded expert.

SPECT/CT or CTPA should be used to verify PE in an emergency manner if clinical suspicion appeared. An autopsy must be performed in all died patients to verify the absence of DVT and PE.

In case of any clinical suspicion for a VTE event, IPC should be interrupted until final verification of the diagnosis. In the case of positive DUS, CTPA, and SPECT/CT, the therapeutic anticoagulation should be prescribed, and IPC should be removed. In the case of clinical suspicion for VTE with negative results of instrumental tests, IPC should not be returned until the proper diagnosis that mimics VTE will be found.

Any revealed leg skin lesion should be judged individually for the possibility to continue ECS and IPC application. If the decision will be made to stop IPC, the patient should be withdrawn from the study according to the protocol.

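### The exclusion for more than 5 days without anticoagulation cannot be judged before allocation, and section 4.2 removes such patients from an analysis that section 8 calls intention-to-treat

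*Combined protocol and SAP*

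**What the plan says.** All references are to the combined protocol and SAP.

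- **Order of events (section 3.1).** "After screening, only eligible patients will be randomized".
- **When screening happens (section 3.2).** "In the case of elective surgery, patients will be screened 1 day before the intervention"; "in case of emergency surgery, just before or within 12 h after the intervention".
- **Exclusion list (section 3.2, after the inclusion criteria).** It contains "postoperative anticoagulation needed at therapeutic doses; absence of anticoagulation", the second item being qualified as more than 5 days after surgery.
- **Withdrawal (section 3.3).** The reasons end with "the occurrence of any exclusion criteria after randomization". The same list separately names any VTE event and calls it a primary or secondary endpoint.
- **Enoxaparin (section 4.2).** The first injection may be delayed for 5 days when bleeding risk is highest. Patients who have not received enoxaparin after that are withdrawn from the analysis.
- **Primary endpoint (section 3.5).** "asymptomatic venous thrombosis of the lower limbs detected by DUS during inpatient treatment".
- **After a positive test (section 5.4).** "the therapeutic anticoagulation should be prescribed, and IPC should be removed".
- **Analysis (section 8).** The primary analysis is intention-to-treat with a two-tailed Fisher's exact test. The ITT set is not defined further. A per-protocol analysis leaves out gross violations and early discontinuation of any component of prophylaxis.

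**The concern.** An exclusion criterion should be something that can be answered before allocation. The 5-day item cannot be: its answer arrives after day 5, when the patient has long been allocated. In practice it is a rule for removing randomised patients, and section 4.2 says so outright by taking them out of the analysis. Section 8 promises an intention-to-treat comparison and does not mention this removal.

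The trial is open-label. When to start LMWH is a bleeding-risk judgement by staff who can know the arm, and only the ultrasound assessor is blinded. If the judgement differs by arm, and if patients whose start is delayed differ in thrombosis risk, the retained groups are no longer the randomised groups. Delayed start is not treated as a rarity: the sample was doubled so that early and delayed LMWH starters could be analysed separately.

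There is also a lesser wording problem. A patient with a positive scan is to receive therapeutic anticoagulation and so literally meets the exclusion item on therapeutic doses after surgery. Nothing in the text exempts anticoagulation started because of a trial-detected event.

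**Working it through.** **1. The plan's own figure.** Section 8 gives 90 per arm for 30% v 12% (18 points absolute, 60% relative), 80% power and a type I error of 0.05. The continuity-corrected two-proportion formula, two-sided, gives 90 per arm. Exact enumeration of the two-sided Fisher test gives 81.2% power at 90 per arm. Then 180/0.90 = 200, doubled to 400, or 200 per arm. The sample size reproduces and is not at fault.

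**2. Timing.**

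| Step | Latest time | Section |
|---|---|---|
| Screening, elective | 1 day before surgery | 3.2 |
| Screening, emergency | 12 h after surgery | 3.2 |
| Allocation | follows a finding of eligibility | 3.1 |
| First scheduled scan | day 3–5 | 5.4 |
| 5-day item can be answered | after day 5 | 3.2, 4.2 |

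The last row falls after the screening window in every case. At least one scheduled scan is due before the item can be applied.

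**3. Consequence.** Section 3.3 makes a later exclusion criterion a withdrawal, and section 4.2 makes lack of enoxaparin after 5 days a removal from the analysis. Section 8 analyses by intention to treat. The last two cannot both hold for the same patient. The wording also differs: section 3.2 speaks of anticoagulation in general, section 4.2 of enoxaparin.

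**4. How large could the bias be?** The documents give neither the share of patients removed nor their event risk, so these are assumed. Take no true effect and 30% risk in both arms. If a share f is removed at 45% risk, the kept risk is (0.30 − f × 0.45)/(1 − f).

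- f = 0.05: 0.2775/0.95 = 29.2%
- f = 0.10: 0.255/0.90 = 28.3%
- f = 0.15: 0.2325/0.85 = 27.4%

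With 5% of controls and 10–15% of IPC patients removed, the spurious relative risk is 28.3/29.2 = 0.97 to 27.4/29.2 = 0.94. With the shares reversed it is 29.2/28.3 = 1.03 to 29.2/27.4 = 1.07, so the direction is not fixed. Equal removal at equal risk gives 1.00.

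A harsher range starts from 200 per arm and removes patients from one arm only, again with no true effect:

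| Removed | Their risk | False difference | Relative risk | Fisher type I error |
|---|---|---|---|---|
| 5% | 45–60% | 0.8–1.6 points | 0.97–0.95 | 4.7–5.7% |
| 10% | 45–60% | 1.7–3.3 points | 0.94–0.89 | 5.8–10.1% |
| 20% | 45–60% | 3.8–7.5 points | 0.88–0.75 | 11.0–33.6% |

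**5. The therapeutic-dose item.** At the planned rates, 200 × 0.30 = 60 control and 200 × 0.12 = 24 IPC patients, 84 in all, would have the primary event and then literally meet this item. That counts an overlap in wording. It is not a predicted loss.

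**The case against.** A reader might infer that both criteria can be known only after allocation, that every primary event makes its patient ineligible, and that eligibility is therefore decided by outcome. The documents do not support that reading.

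- A need for therapeutic anticoagulation can be foreseen at screening. The item follows directly on the exclusion for regular preoperative anticoagulation, and emergency patients may be screened up to 12 h after surgery.
- Section 3.3 calls a VTE event an endpoint. Section 3.4, which lists deviations that remove a patient from the final analysis, names neither VTE nor therapeutic anticoagulation, although it closes with an open-ended item. The Cox model in section 8 uses the time of VTE registration. No passage drops patients with VTE from the primary analysis, and dropping all of them would leave no events to compare.

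On the 5-day item, three points can be made in the plan's defence. The delay is tied to the highest bleeding risk, and nothing shows that this differs by arm. A patient with a positive scan by day 5 should be receiving therapeutic anticoagulation, so reading the scan first does not in itself select event patients for this exclusion. And the milder scenario gives 0.94–0.97, small beside the planned relative risk of 12/30 = 0.40.

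These points limit the likely size, and the first two make the assumed 45% risk and unequal shares uncertain. They do not answer the contradiction: an analysis that withdraws randomised patients for what happened after allocation is not intention-to-treat, whatever the size of the bias.

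**Conclusion.** The concern holds for the 5-day item. It cannot be assessed when eligibility is settled, sections 3.3 and 4.2 turn it into a removal after randomisation, and this contradicts section 8. The conclusion rests on the text and needs no assumed figure.

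The size of any bias is unknown. It requires removal that differs between arms in frequency or in event risk. Under the assumed 5% v 10–15% at 45% risk it is a relative risk of 0.97–0.94 where the truth is 1. It becomes serious only if removal is heavy and one-sided, such as 20% of one arm.

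The therapeutic-dose item is a wording gap. It coincides with the primary event and lacks an exemption, but the text does not say that these patients leave the analysis.

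**What to change.** - **Section 3.2.** Limit the exclusion list to conditions known or planned before allocation, and reword the two anticoagulation items accordingly.
- **Section 3.3.** State that the same conditions arising after randomisation, including anticoagulation started for a trial-detected VTE, may end study treatment but do not make a randomised patient ineligible. The patient stays in the ITT set in the allocated arm, with events counted.
- **Sections 4.2 and 8.** Reconcile the two by confining the section 4.2 removal to the per-protocol analysis, which already leaves out early discontinuation of a component. Define the ITT set in section 8 and use the same term for the drug in sections 3.2 and 4.2.

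Rewording section 3.2 alone would leave the section 4.2 removal in force, so the changes belong together. They imply no change to treatment and no new sample size.

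The cost is a few sentences and perhaps a slight dilution of the effect estimate from patients whose prophylaxis was not as planned. There is room for that in the main comparison: at the planned rates, exact Fisher power is 99.3% with 200 per arm and 98.6% with 180.

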### **3.3. Patient's withdrawal from the study**

Patient's withdrawal from the study will be possible in case of the patient's refusal from further participation, the occurrence of serious adverse events necessitating early termination of study procedures, as well as meeting the criteria for patient's withdrawal from the study. The criteria for withdrawal are as follows: the occurrence of any VTE event, considered as a primary or secondary endpoint; the occurrence of major or non-major clinically relevant bleeding, considered as secondary endpoints, required the discontinuation of LMWH administration; the occurrence of leg skin injury, considered as a secondary endpoint; required discontinuation of IPC application; the occurrence of any clinical condition required discontinuation of IPC or ECS application (e.g., leg ischemia, compartment syndrome); the occurrence of any clinical condition that required discontinuation of LMWH administration (e.g., thrombocytopenia, allergic reaction); the occurrence of any clinical condition that required changes in the VTE prophylaxis modality (e.g., change in dose and type of anticoagulation); and the occurrence of any exclusion criteria after randomization.

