### **Secondary objectives:**

- To study the effect of IPC on the asymptomatic venous thrombosis occurrence during inpatient treatment in prespecified groups of patients:
  - Surgical profile,
  - Type of surgery,
  - The urgency of surgery,
  - The radicalism of surgery,
  - Type of anesthesia,
  - Malignant or benign disorder;
  - Preoperative, postoperative or delayed start of LMWH injections,
  - Pre-operative or post-operative IPC application,
- To study the effect of IPC on the isolated calf muscle DVT occurrence during inpatient treatment;
- To study the effect of IPC on the proximal DVT occurrence during inpatient treatment;
- To study the effect of IPC on the symptomatic PE occurrence during inpatient treatment;
- To study the effect of IPC on the fatal PE occurrence during inpatient treatment,

- To study the effect of IPC on the total VTE events that occur during inpatient treatment,
- To study the effect of IPC on the leg skin injury occurrence during inpatient treatment;
- To study the effect of IPC on the major and clinically relevant non-major bleeding occurrence during inpatient treatment;
- To study the compliance with IPC applied in the suggested regimen-required night free-of-compression interval;
- To study the effect of IPC on the symptomatic and asymptomatic venous thrombosis of lower limbs, symptomatic pulmonary embolism occurrence, and VTE related and VTE-non-related mortality during outpatient treatment and rehabilitation 30 and 180 days after surgery.

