#### **Secondary endpoints:**

During inpatient treatment: isolated calf muscle DVT; proximal DVT; symptomatic PE; fatal PE; total VTE events; postoperative mortality; leg skin injury; combination of major and clinically, relevant non-major bleeding; and compliance with IPC.

At 30 days after surgery:

- Combination of symptomatic, asymptomatic venous thrombosis of the lower, limbs and symptomatic PE;
- VTE-related mortality;
- Non-VTE-related mortality.

At 180 days after surgery:

- Combination of symptomatic, asymptomatic venous thrombosis of the lower limbs, and symptomatic PE;
- VTE-related mortality;
- Non-VTE-related mortality.

Following DUS, distal DVT is defined as incompressibility of the affected calf vein, re-occlusion of the previously affected calf vein in case of personal DVT history. Proximal DVT is defined as incompressibility of the affected popliteal and thigh veins, re-occlusion of previously affected popliteal and thigh veins in case of personal DVT history, no blood flow with color flow imaging. Superficial vein thrombosis is defined as incompressibility of the affected superficial vein (GSV and its branches and SSV and its branches). Isolated calf muscle DVT is defined as occlusion of any calf veins except PTV, ATV, and PeV (sural veins, soleal veins). Proximal DVT is defined as occlusion of popliteal and all further cranial venous segments up to the iliac veins (PV, FV, CFV, external iliac vein, common iliac vein). Pulmonary embolism will be suspected according to the classical clinical symptoms and verified with SPECT/CT or CTPA by specific defects of contrast.

Major bleeding is defined by the ISTH criteria as: fatal bleeding; bleeding that is symptomatic and occurs in a critical area or organ; extra-surgical site bleeding causing a fall in hemoglobin level of  $\geq 20$  g/L, or leading to transfusion of  $\geq 2$  units of whole blood or RDC, with temporal association within 24–48 h to the bleeding; surgical site bleeding that requires a second intervention; or surgical site bleeding that is unexpected and prolonged or sufficiently large to cause hemodynamic instability, as assessed by the surgeon.

Clinically relevant non-major (CRNM) is defined as any other bleeding, that does not match the criteria of major but needs some specific measures for hemostasis and/or interruption or preliminary abortion of anticoagulation.

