## 8. Statistical analysis plan and sample size calculation

**Statistical analysis plan.** The primary statistical analysis is designed as intention-to-treat with the use of two-tailed Fisher's exact test to compare the primary endpoint between two groups. The primary endpoint will be reported as an absolute number, percentage, and relative risk with 95% CI. Secondary statistical analysis of the primary endpoint will be made using an unadjusted Cox proportional-hazards model. The data will be censored on the time of VTE registration, or death, or discharge from the hospital and reported as a hazard ration with 95% CI. Kaplan-Meier curves will be used to compare time-to-event distribution. Cox proportional-hazards models adjusted for the clinical center, surgery profile, type of surgery, emergency of surgery, type of anesthesia, surgical radicalism, malignant disorder, Caprini score, and time to start LMWH injections will be used.

A similar analysis for the per-protocol population, but that excluded patients with gross violations of the protocol and premature discontinuation of at least one component of combined prophylaxis (ECS, IPC or LMWH), will be performed for the primary endpoint.

Secondary endpoints will be analyzed with two-tailed Fisher's exact test and will be represented as an absolute number, percentage, and relative risk with 95% CI.

Cox proportional-hazards models will be used for the prespecified subgroup analysis for the following subgroups: surgical profile; type of surgery; the urgency of surgery; the radicalism of surgery; type of anesthesia; malignant or benign disorder; preoperative, postoperative, or delayed start of LMWH injections; and pre-operative or post-operative IPC application.

Sensitivity analysis will address to the per-protocol analysis, compliance with IPC (restricted for 90% and more), duration of follow-up (restricted to 7 days and more), and the number of postoperative DUS (restricted with two and more).

Missing data on the primary endpoint are not anticipated in the inpatient settings, so no analysis for missing data being planned.

Adjusting for multiple comparisons and imputation for missing values will not be performed. The 95% confidence intervals will be not adjusted for multiplicity, and therefore, inferences drawn from these intervals might be not reproducible. The interim analysis is not planned.

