**Sample size calculation.** The prevalence of asymptomatic postoperative vein thrombosis at the top of standard prophylaxis with ECS and LMWH was assumed as 30% based on our previous observations involving patients at high and extremely high risk. Taking into account the fact that pharmaco-mechanical prophylaxis should provide a further 60% VTE risk reduction, the absolute difference of 18% is assumed. Using Fisher's exact test for primary statistic analysis, with a power of 80% and type I error of 0.05, the sample size is estimated as 180 subjects (90+90 in each group). Assuming 10% withdrawal due to the protocol deviations, patient's decision, or incomplete data, the sample size is calculated as 200 subjects. Considering prespecified subgroup analysis for the patients with an early and delayed start of LMWH, we decided to double the sample size to achieve sufficient power for separate analyses of the suggested subgroups. IBM SPSS will be used for data processing.

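### A VTE event is a criterion for leaving the study and no later follow-up is stated, so subsequent PE, proximal extension, bleeding and deaths may go unrecorded, unequally by arm at the plan's own rates

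*Combined protocol and SAP*

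**What the plan says.** Section 3.3 is about leaving the study, not only about stopping the study prophylaxis. It opens permissively: "Patient's withdrawal from the study will be possible in case of the patient's refusal from further participation", and it then adds serious adverse events and a list of criteria. The first criterion is "the occurrence of any VTE event, considered as a primary or secondary endpoint". The list also covers stopping IPC, stockings or LMWH, a change of prophylaxis, and any exclusion criterion that arises after randomisation.

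Section 3.5 names as separate inpatient endpoints "isolated calf muscle DVT; proximal DVT; symptomatic PE; fatal PE; total VTE events; postoperative mortality", together with bleeding. It adds VTE-related and other mortality at days 30 and 180. The secondary objectives in section 2 likewise include "symptomatic pulmonary embolism occurrence, and VTE related and VTE-non-related mortality during outpatient treatment and rehabilitation 30 and 180 days after surgery". Section 3 promises six months of follow-up, and section 5.5 sets contacts at days 30 and 180.

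For the analysis, section 8 states "Secondary endpoints will be analyzed with two-tailed" Fisher's exact tests. It plans no imputation and no competing-event method. Its remark that missing data are not expected covers only the inpatient primary endpoint.

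**The concern.** The efficacy outcome is itself a reason to leave the study. Under section 5.4, scans are repeated every 3–5 days, so silent thromboses will be found, and the criterion met, during the hospital stay. If such a patient then leaves, a later extension into the proximal veins, PE, bleed or death has no stated route into the data. Yet the comparison of each secondary endpoint reads as if every randomised patient had been observed for it.

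The patients concerned are plausibly those at highest risk of a further event, and the plan expects more of them in the control arm. A treatment that prevents first thromboses would keep more of its patients under observation, and so have more of its later events counted. Its effect on PE and death could be hidden or could appear reversed.

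**Working it through.** **Inputs**

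- Control rate, section 8: "at the top of standard prophylaxis with ECS and LMWH was assumed as 30" per cent.
- Effect, section 8: a 60% relative reduction, so "the absolute difference of 18% is assumed". The IPC rate is 0.30 − 0.18 = 0.12.
- Error rates, section 8: "with a power of 80% and type I error of 0.05". The test is two-sided.
- Size, section 8: 90 + 90, raised to 200 for 10% withdrawal, then doubled. The total of 400 (200 per arm) is implied but not printed.
- Risk of a later event with or without a first thrombosis: not given, so assumed below.

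**The plan's own figure**

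The two-proportion formula without continuity correction gives

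(1.960 × √(2 × 0.21 × 0.79) + 0.842 × √(0.30 × 0.70 + 0.12 × 0.88))² / 0.18² ≈ 79.2, so 80 per arm.

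With the correction, (79.2/4) × (1 + √(1 + 4/(79.2 × 0.18)))² ≈ 90 per arm, or 180 in total, as stated. Exact power of Fisher's test at 90 per arm is 81.2%. Then 180/0.90 = 200, also as stated.

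**Patients meeting the VTE criterion through a primary event**

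- Control: 0.30 × 200 = 60. IPC: 0.12 × 200 = 24. The ratio is 2.5 to 1.
- Together 84/400 = 21%, leaving 140 and 176 if all of them left.
- The 10% allowance covers 40 of 400. Its stated reasons do not include VTE.

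| Control rate | Relative reduction | Control | IPC | Limiting RR if counted event-free |
|---|---|---|---|---|
| 30% | 0% | 60 | 60 | 0.70/0.70 = 1.00 |
| 30% | 20% | 60 | 48 | 0.76/0.70 = 1.09 |
| 30% | 40% | 60 | 36 | 0.82/0.70 = 1.17 |
| 30% | 60% | 60 | 24 | 0.88/0.70 = 1.26 |
| 10% | 60% | 20 | 8 | 0.96/0.90 = 1.07 |
| 20% | 60% | 40 | 16 | 0.92/0.80 = 1.15 |

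The imbalance exists only if IPC prevents first thromboses.

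**Effect on a later endpoint**

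Let the later risk be r without a first thrombosis, equal in both arms, and k × r after one.

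- True RR = (0.12k + 0.88)/(0.30k + 0.70).
- Later events unseen and patients kept in the denominator: 0.88r/0.70r = 1.26. Both r and k drop out.
- Patients dropped from the denominator: r/r = 1.0.

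| k (assumed) | True RR | Control events missed | IPC events missed |
|---|---|---|---|
| 1 | 1.00/1.00 = 1.00 | 0.30/1.00 = 30% | 0.12/1.00 = 12% |
| 2 | 1.12/1.30 = 0.86 | 0.60/1.30 = 46% | 0.24/1.12 = 21% |
| 5 | 1.48/2.20 = 0.67 | 1.50/2.20 = 68% | 0.60/1.48 = 41% |

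The value 1.26 is the limit of complete loss. If half of the later events were still captured, k = 5 would give (0.30 + 0.88)/(0.75 + 0.70) = 0.81 against a true 0.67.

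In counts, take r = 2% and k = 5 at 200 per arm. True expected events are 0.044 × 200 = 8.8 in control and 0.0296 × 200 = 5.9 with IPC. Those observed are 0.014 × 200 = 2.8 and 0.0176 × 200 = 3.5.

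**Would removing the VTE clause alone be enough?**

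No. Section 5.4 says that a positive test leads to therapeutic anticoagulation and removal of IPC. That still meets the 3.3 criterion on changed prophylaxis. It also meets the criterion on exclusion conditions arising after randomisation, because section 3.2 excludes patients who need therapeutic-dose anticoagulation after surgery.

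**The case against.** The strongest reply is that the text never says these patients are lost. Withdrawal is worded as possible, not automatic. Section 5.4 requires an autopsy after every death. Section 5.5 makes no exception for patients with a VTE and allows a telephone contact. Section 3.4 does not list VTE among the deviations that remove a patient from the final analysis. A 10% allowance beside an expected 21% with thrombosis fits better with a plan that keeps them. This stands as a reason not to treat the loss as certain. It does not close the gap: no section states that follow-up continues, and discretion without a rule, in an open-label trial, is itself a risk. The autopsy rule sits in the inpatient section and captures no non-fatal PE.

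Several stronger readings are tempting and are not supported.

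- A reader might infer that the primary result is biased. It is not biased by this route, because the event is recorded before the patient could leave.
- A reader might infer that total VTE is hidden. Counted per patient, it already includes the first event, as does the day-30/180 VTE composite if it accumulates from surgery, which the text does not specify. A PE or proximal DVT that is the first event, or is found together with another thrombosis, is also recorded.
- A reader might suppose that most first events are small calf thromboses. No section gives their distribution.
- A reader might conclude that the control arm loses more patients overall. The calculation covers VTE-triggered withdrawal only. Sections 3.3 and 5.4 also withdraw patients whose IPC is stopped, at a rate not given, which could offset part of the difference.

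It is also fair that the apparent reversal is less than one expected event (2.8 versus 3.5), that the post-thrombosis risks are assumed and would apply under therapeutic anticoagulation, and that the bias would not create a false benefit for IPC.

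**Conclusion.** The concern holds for events after a first thrombosis: later proximal extension, symptomatic or fatal PE, bleeding, and inpatient, 30-day and 180-day deaths. Section 3.3 as written permits these patients to leave the study, and nothing provides for their follow-up, while sections 2, 3, 3.5 and 5.5 require those outcomes.

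At the assumed 30% versus 12% and 200 per arm, about 60 and 24 patients are exposed. With complete loss, the observed RR tends to 1.26 or 1.0, according to the denominator. This rests on the plan's effect size, equal later risk in both arms without a prior thrombosis, and no offset from IPC-specific withdrawals. How much would be lost in practice cannot be determined from the documents, so they do not show that the PE or mortality result will be reversed.

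Severity: should-fix. Only secondary endpoints are affected, but outcomes not collected cannot be recovered by analysis.

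**What to change.** In section 3.3, separate stopping study prophylaxis from leaving the study. Apply this to every listed criterion, including the VTE clause and those on changed prophylaxis, stopping IPC or LMWH, and exclusion criteria arising after randomisation. State that only withdrawal of consent ends follow-up, and that a VTE event ends time at risk for the primary time-to-event analysis only.

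Keep these patients in inpatient outcome recording and in the day-30 and day-180 contacts. In section 8, count each secondary endpoint per randomised patient whether or not a VTE came first, and flag events after the switch to therapeutic anticoagulation. Reconcile sections 3, 3.3, 5.4, 5.5 and 8. Clinical management after a VTE stays as the protocol describes it.

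The cost is protocol wording and some further contacts of a kind already scheduled; the primary sample size does not change. The drawback is that later outcomes are seen under therapeutic anticoagulation, which the flag makes visible but does not remove.
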